12.2.1 Hematology

Parameters include hematocrit, hemoglobin, mean corpuscular hemoglobin, mean corpuscular hemoglobin concentration, mean corpuscular volume, platelet count (available at EOS/ET only), red blood cell count and white blood cell count with differential. Visits include Screening (or EOS Visit RB-US-13-0003) and Day 169 Week 25 (EOS INDV-6000-301) /ET visit.

12.2.2 Serum Chemistry

Parameters include albumin, ALP, ALT, amylase, AST, blood urea nitrogen, calcium, calculated creatinine clearance, carbon dioxide, chloride, creatinine, creatinine kinase and subtypes, gamma-glutamyl transferase, globulin, glucose (non-fasting), high-density lipoprotein, lactate dehydrogenase, lipase, low-density lipoprotein, magnesium, phosphorus, potassium, sodium, total bilirubin, direct bilirubin, total cholesterol, total protein, triglycerides and uric acid. Visits include EOS Visit RB-US-13-0003 and Day 169 Week 25 (EOS INDV-6000-301)/ET visit.

12.2.3 Urinalysis

Parameters include appearance, bilirubin, color, glucose, ketones, leucocyte esterase, nitrite, occult blood, pH, protein, specific gravity and urobilinogen.

Microscopic examination of sediment will be performed only if the results of the urinalysis evaluation are positive. Microscopic examination also includes but not limited to WBC count, RBC count, casts, and crystals. The microscopic results will be listed only.

12.3 VITAL SIGNS

Measurements of vital signs (supine blood pressure systolic, supine blood pressure diastolic, pulse rate, oral temperature, respiratory rate, pulse oximetry, weight, height, BMI, hip circumference, waist circumference and waist-to-hip ratio) will be summarized using descriptive statistics at each scheduled visit and time point including change from baseline, percentage change from baseline and pre- and post- injection change if available.

Listings/tables of all vital sign assessments will be provided for the following groups:

- Supine blood pressure systolic, Supine blood pressure diastolic, Pulse rate, Oral temperature, and Respiratory rate, Pulse Oximetry;
- Body weight, BMI, Hip Circumference, Waist Circumference and Waist-to-hip ratio.

12.4 OTHER SAFETY PARAMETERS

12.4.1 Suicidality

A listing of all results will be presented for all subjects for all visits.

Table summaries will be run twice with two different baseline definitions:

- “Baseline Lifetime” will use the answers for suicidality (lifetime) in the screening/baseline questionnaire.
- “Baseline 6 months” will use the answers for suicidality (in the past 6 months) in the screening/baseline questionnaire.

Suicidal Ideation Severity Scoring

The suicidal ideation score ranges from 0 to 5 and depends on the answers to the suicidal ideation portion of the C-SSRS. The score is the maximum suicidal ideation category (in the following order: 1 = wish to be dead, 2 = non-specific active suicidal thoughts, 3 = active suicidal ideation with any methods (not plan) without intent to act, 4 = active suicidal ideation with some intent to act, without specific plan, and 5 = active suicidal ideation with specific plan and intent) present at the assessment. If none of these questions are YES, then the suicidal ideation score is 0.

Suicidal Ideation Intensity Scoring

The suicidal ideation intensity score is the sum of the five intensity item scores to create a total score (range 0 to 25). The five intensity items include frequency, duration, controllability, deterrents and reason for ideation. Each item is scored from 0 to 5 with 5 representing the most severe intensity.

Suicidal Behavior Scoring

The suicidal behavior score ranges from 0 to 5 and depends on the answers to the suicidal behavior portion of the C-SSRS. The score is the maximum suicidal behavior category (in the following order: 1 = preparatory acts or behavior, 2 = aborted attempt, 3 = interrupted attempt, 4 = actual attempt, and 5 if the subject has an AE with a preferred term of completed suicide. If none of these questions are YES and the subject does not have an AE with a preferred term of completed suicide, then the suicidal behavior score is 0.

Suicidal ideation and suicidal behavior responses (Yes/No) will be summarized by analysis visit using counts and percentages in the Safety Analysis Set. Shift tables to demonstrate changes in C-SSRS categories and changes in suicidal ideation and behavior scores from baseline during the Treatment Period will be presented. CSSRS and suicidal ideation responses will be listed separately. The suicidal ideation intensity ratings, each of the five items and the total score of the intensity for subjects with an ideation will be listed.

12.4.2 Local Injection Site Evaluation

The local injection site will be evaluated for potential reaction and evidence of any attempts by the subject to remove RBP-6000 following a previous injection. A summary table and a listing will be provided. Attempted removal results will be summarized by percentage of subjects with attempted removal in each dose received at each visit.

12.4.3 Local Injection Site Tolerability

Local injection site tolerability as assessed by the Injection Site Grading scale will be summarized and plotted over time by category (pain, tenderness, erythema/redness, induration, and swelling) and severity using frequency counts and percentages. Local injection site tolerability will be assigned a severity grade, including none (grade 0), mild (grade 1), moderate (grade 2), severe (grade 3), or potentially life threatening (grade 4) utilizing the 5-point Injection Site Grading Scale. A listing will be provided.

A separate listing will be presented for severe/life threatening responses with their corresponding VAS scores.

12.4.4 Injection Site Pain

Injection Site Pain VAS scores will be summarized over time during the Treatment Period. And the maximum score during the Treatment Period will be calculated and tabulated. The burning/stinging categorical variable (Yes/No) will be summarized by percentage of responses in each dose received at each time point.

The percentage of subjects who reported injection site reaction (Yes) at each injection visit in the Safety Analysis Set. Mean value of local injection site VAS pain scores will also be plotted at each injection.

Separate listings for burning/stinging will be provided. A listing of injection site pain VAS scores will also be provided.

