#### 9.5.1.4 Other Variables Related to Safety

Medical history will be coded using MedDRA and summarized by treatment group as described for AEs ([Section 9.5.1.1](#)). Body weight, height, BMI, and abdominal fat measurement (waist-to-hip ratio) will be summarized using descriptive statistics (mean, median, SD, minimum, maximum), including change from baseline.

Total C-SSRS scores will be summarized using descriptive statistics (mean, median, SD, minimum, maximum), including change from baseline.

Prior and concomitant medications will be coded using the most recent version of the World Health Organization (WHO) Drug dictionary. Incidence (number and percent of subjects reporting the medication at least once during the study) will be summarized for all concomitant medications.

Local injection site tolerability as assessed by the Injection Site Grading scale will be summarized by category and severity using frequency counts and percentages similar to summaries for AEs ([Section 9.5.1.1](#)). Injection Site Pain VAS scores will be summarized by dose and injection. The burning/stinging categorical variable (Yes/No) will be summarized by percent of responses for each dose.

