6.3 TREATMENT GROUPS

There is only one treatment group in the trial and all subjects will be labeled with “RBP-6000 (100/300 mg Flex)”.

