20.10 C-SSRS DATA IMPUTATION

In the Suicidal Behavior section, when the answer to the question "Have you made a suicide attemp" is NO, then the "Total # of Attempts" should be 0. In our clincial database, we have both 0 and Blank present. In the analysis dataset, under this scenario, Blank for Total # of Attempts will be imputed as 0.

No changes have been made to analyses specified in protocol.

22.0 **REFERENCES**

Guidance for Industry Drug-Induced Liver Injury: Premarketing Clinical Evaluation:
U.S. Department of Health and Human Services Food and Drug Administration Center
for Drug Evaluation and Research (CDER) Center for Biologics Evaluation and
Research (CBER)

23.0

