Table 14.3.1.15 Summary of Treatment-Emergent Adverse Events Potentially Pertaining to Acute Pancreatitis by MedDRA System Organ Class and Preferred Term during the Treatment Period - Safety Analysis Set

Table 14.3.1.16 Summary of Treatment-Emergent Adverse Events Potentially Pertaining to Hepatic Disorders by MedDRA System Organ Class and Preferred Term during the Treatment Period - Safety Analysis Set

Table 14.3.1.17 Summary of Treatment-Emergent Adverse Events Potentially Pertaining to Respiratory Depression and Failure by MedDRA System Organ Class and Preferred Term during the Treatment Period - Safety Analysis Set

Table 14.3.1.18 Summary of Treatment-Emergent Adverse Events Potentially Pertaining to Central Nervous System Depression by MedDRA System Organ Class and Preferred Term during the Treatment Period - Safety Analysis Set

Table 14.3.1.19 Summary of Treatment-Emergent Adverse Events Potentially Pertaining to Orthostatic Hypotension by MedDRA System Organ Class and Preferred Term during the Treatment Period - Safety Analysis Set

Table 14.3.1.20 Summary of Treatment-Emergent Adverse Events Regarding Psychiatry History Topic by MedDRA System Organ Class and Preferred Term during the Treatment Period - Safety Analysis Set

Table 14.3.2.1 Early Removal of Study Drug Depot – Safety Analysis Set

Table 14.3.3.1 Summary of Local Injection Site Tolerability Reactions During the Treatment Period- Safety Analysis Set

Figure 14.3.3.1 Percentage of Subjects Who Reported Local Injection Site Tolerability Reactions: Pain - Safety Analysis Set

Table 14.3.3.2 Summary of Local Injection Site Visual Analog Scale (VAS) Pain Scores - Safety Analysis Set

Figure 14.3.3.2 Mean Value of Local Injection Site Visual Analog Scale (VAS) Pain Scores by visit - Safety Analysis Set

Table 14.3.3.3 Summary of Local Injection Site Burning/Stinging Evaluation - Safety Analysis Set

Table 14.3.3.4 Summary of Injection Site Evaluation During the Treatment Period: Attempted Removal - Safety Analysis Set

Table 14.3.4.1 Incidence of Columbia Suicide Severity Rating Scale (C-SSRS): Suicidal Ideation and Suicidal Behavior - Safety Analysis Set

Table 14.3.4.2 Shift Table to Demonstrate Change in C-SSRS Categories from Baseline Lifetime During the Treatment Period - Safety Analysis Set

Table 14.3.4.3 Shift Table to Demonstrate Change in C-SSRS Categories from Baseline 6 months During the Treatment Period - Safety Analysis Set

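### SAP 12.4.4 omits the by-dose summary of injection-site pain VAS that protocol 9.5.1.4 specifies, while SAP 21.0 declares no changes to the protocol analyses

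*SAP*

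**What the plan says.** Protocol 9.5.1.4 states: "Injection Site Pain VAS scores will be summarized by dose and injection". It also asks for the Yes/No burning/stinging item for each dose.

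For the same VAS score, SAP 12.4.4 states: "Injection Site Pain VAS scores will be summarized over time during the Treatment Period". It continues: "And the maximum score during the Treatment Period will be calculated and tabulated", and later: "Mean value of local injection site VAS pain scores will also be plotted at each injection". No dose is named in any of the three. In the same paragraph the burning/stinging item is to be "summarized by percentage of responses in each dose received at each time point".

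SAP 6.3 sets the default display: "There is only one treatment group in the trial and all subjects will be labeled with" one flexible-dose label covering 100 mg and 300 mg.

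SAP 21.0 states: "No changes have been made to analyses specified in protocol". Protocol 9.1 had said that departures from the analyses it describes would be set out in the SAP.

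**The concern.** The protocol's rule for VAS has two parts, dose and injection. The SAP keeps the second and drops the first without saying so.

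Injection-site grading, which includes pain graded by site staff, is not split by dose in either document. VAS was therefore the only measure of pain severity that the protocol planned to show by dose. Without it, the SAP's only by-dose information on how the injection feels is a Yes/No answer on burning or stinging.

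The protocol lets the Investigator choose 100 mg or 300 mg at each injection and move a subject up or down during the study (sections 1.2 and 5.4). A single mean per visit therefore reflects both the pain at each dose and the share of subjects on each dose at that visit. A reader of the overall row cannot separate the two.

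The declaration in SAP 21.0 is a second matter. A reader who relies on it would not look for a missing protocol analysis.

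**Working it through.** The plan gives no figure to reproduce here: there is no test, power calculation or target difference for VAS. The check is a comparison of text, followed by a short illustration.

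**Step 1: set the specifications side by side.**

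| Item | Protocol 9.5.1.4 | SAP text | Split by dose in the SAP |
|---|---|---|---|
| VAS pain | by dose and by injection | 12.4.4: over time, maximum, mean plotted per injection | absent |
| Burning/stinging | for each dose | 12.4.4: per dose received, each time point | kept |
| Injection-site grading | category and severity, no dose | 12.4.3: category and severity, over time, no dose | never planned |
| Attempted depot removal | not mentioned | 12.4.2: per dose received, each visit | added by the SAP |

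Only the VAS row shows a split that the protocol specified and the SAP does not.

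**Step 2: could dose be implied?** SAP 6.3 puts all subjects under one label, so a split does not arise by default. Where the SAP wants a split, its text says so: exposure and depot removal (10.1), dose level by visit (10.2), attempted removal (12.4.2) and burning/stinging (12.4.4). The last comes directly after the VAS maximum. The natural reading is that VAS is summarised over both doses together. This is an inference: 12.4.4 does not state it, and the table shells are not in the documents.

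**Step 3: do the table titles help?** The title of Table 14.3.3.2, "Summary of Local Injection Site Visual Analog Scale (VAS) Pain Scores - Safety Analysis Set", names no dose. Neither do the titles of Table 14.3.3.3 (burning/stinging) and Table 14.3.3.4 (attempted removal), which the SAP text does split by dose. The titles are therefore not evidence either way.

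**Step 4: what an overall mean can hide.** Let m100 and m300 be the mean VAS at each dose, d = m300 − m100, and s the share of injections at 300 mg. Then

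overall mean = (1 − s) × m100 + s × m300 = m100 + s × d.

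The documents give neither the dose mix nor any VAS mean, so d and s are assumed. With d = 10 mm:

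- s = 0.5: the overall mean lies 5 mm above m100 and 5 mm below m300
- s = 0.7: 7 mm above and 3 mm below
- s = 0.9: 9 mm above and 1 mm below

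If s moves by 0.2 between visits, the overall mean moves by 0.2 × 10 = 2 mm with no change in pain at either dose. If s moves from 0.5 to 0.9, it moves by 0.4 × 10 = 4 mm. The movement is proportional to d: for the 0.2 shift, half the assumed difference (5 mm) gives 1 mm and twice (20 mm) gives 4 mm. If the doses do not differ in pain, it is zero. On a 100 mm scale these are small movements.

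**The case against.** The best case for the SAP is that very little is missing.

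- Burning/stinging, the second item on the same form, stays by dose, and so does attempted removal. This stands, and it limits the point to one summary. A reader might infer that the comparison of local tolerability between doses is lost altogether. The documents do not support that, and grading was never planned by dose.
- The data remain available. VAS scores are listed (Listing 16.2.19), the dose at each injection is listed (Listing 16.2.8), and the dose mix by visit is tabulated (Table 14.1.6.5). This stands, but a listing is not the summary that the protocol specified.
- The protocol has no dose groups and plans no contrast. A reader might infer that a by-dose table would show whether the 300 mg injection hurts more. It could not show that reliably. The dose is not randomised, and SAP 10.2 names adverse events and a lower-dose strategy among the reasons for changing it, so tolerability may itself drive the dose. This is a reason to label the table descriptive; it does not justify omitting it without comment.
- The shells may already split by dose. That is possible. If so, the text of 12.4.4 needs only to be brought into line with them.
- The illustration rests on assumed values. This is correct: it shows how the overall mean behaves and does not measure an effect in this trial.

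**Conclusion.** The point holds in a narrow form. Protocol 9.5.1.4 specifies VAS by dose and injection, SAP 12.4.4 as written leaves out the dose split, and SAP 21.0 says that nothing changed. This is a mismatch between the two documents and an inaccurate statement. It should be corrected, and it ranks at the modest end.

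It affects one descriptive safety summary and has no bearing on any error rate, the sample size or what is collected. The mismatch itself rests on no assumption. That VAS would be shown for both doses together rests on the wording of 12.4.4 and the single label in 6.3, without sight of the shells.

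A larger injected amount at 300 mg might suggest that pain must differ by dose. The documents give no link between amount and pain, so no size of harm can be stated.

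**What to change.** In SAP 12.4.4 and Table 14.3.3.2, summarise VAS by dose received at that injection (100 mg, 300 mg) and by injection number. Give the number of injections per dose and visit as the denominator and keep the overall column. Add a note that the table is descriptive, because the Investigator chooses the dose and it can change between injections.

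A by-dose version of Figure 14.3.3.2 is optional, since the protocol does not ask for one. The maximum over the Treatment Period is the SAP's own addition and can stay as it is.

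If the split is left out deliberately, state that in SAP 21.0 with the reason, and remove the claim that nothing changed.

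The cost is two dose columns in an existing table and a few words of text. The dose at each injection is already collected and listed, so no new data are needed.

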12.4.5 Other Safety Variables

NA.

12.5 INDEPENDENT DRUG COUNSELING/BEHAVIOURAL THERAPY

A listing for whether independent drug counseling (IDC) was completed per subject visit will be provided.

13.0 POOLED ANALYSES

No pooled analyses will be conducted in this trial.

14.0 SUBGROUP ANALYSES

No subgroup analyses will be conducted in this trial.

15.0

HEALTH OUTCOME ANALYSES

No health outcome assessments were performed in this study.

16.0 PLASMA CONCENTRATION ANALYSES

No plasma concentration samples were collected in this study.

No Interim analysis was performed for this study

18.0 DETERMINATION OF SAMPLE SIZE

This study is designed to provide ongoing treatment with RBP-6000 and to assess the safety monitoring for subjects who complete the RB-US-13-0003 study and for whom a new treatment venue has not been identified or arranged. Approximately 300 subjects who completed Study RB-US-13-0003 will be enrolled into this study.

19.0 COMPUTER METHODS

Statistical analyses will be performed using version 9.4 (or newer) of SAS on a Windows operating system.

20.0 DATA HANDLING CONVENTIONS

20.1 REFERENCE DATES AND ANALYSIS PERIODS

There are two analysis periods in this study:

- Treatment Period (TP)
- Safety Follow-Up Period (SFU).

Treatment Period starts from Treatment Start Date and ends at Treatment End Date. Treatment Start Date (or Day 1) for a subject is the date of the first injection. Treatment End Date for a subject is the maximum of the date of the end-of-study/ Early Termination (EOS/ET) visit and the date of last injection + 28.

Safety Follow-Up Period starts from Safety Follow-Up Start Date and ends at Safety Follow-Up End Date, which are defined for all subject who have assessments in the Follow-Up period.

Safety Follow-Up Start Date for a subject is Treatment End Date +1.

Safety Follow-Up End Date for a subject is defined as the date of visit at Week 29 or unscheduled visit after the Treatment End Date (defined as above) for AE/concomitant medication reporting or lab/vital signs assessment, whichever comes later. That is, Follow-up end date is max (Follow-up Start Date, date of visit at Week 29, last unscheduled visit after the Treatment End Date to report AE/concomitant medication or to do lab/vital signs assessment, if available).

Any records collected prior to first injection date/time will be considered as Screening records. And any records collected after the Treatment End Date will be considered as Safety Follow-up records.

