### 5.3 Selection and Timing of Dose for Each Subject

The study schedule is designed so that each of the injections will be separated by a minimum of 26 days and a maximum of 35 days (28 days -2/+7 days) and will be given on alternate sides of the subject's abdomen (see [Appendix 2](#) and the Pharmacy Manual for detailed information on administration).

If at an Injection Visit there is a safety concern with administration of RBP-6000, dosing can be delayed within the specified window. No injections are permitted outside of this window without prior consent from the Medical Monitor.

Time of dose is defined as the time the RBP-6000 SC injection is complete.

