12.1 ADVERSE EVENTS

12.1.1 Adverse Events

Imputation rules for AE (for determination of TEAE only) start date are in Section 20.7.

Treatment-emergent Adverse Events (TEAEs)

TEAEs are those that started following the first dose of RBP-6000 and before the Treatment End Date (the maximum of the date of the end-of-study/ Early Termination (EOS/ET) visit and the date of last injection + 28 days) in this study, or were present prior to the first dose of RBP-6000 regardless of causality and increased in severity within the treatment period (defined in section 20.1) AEs include those events that are ongoing at the time a subject rolls-over from the RB-US-13-0003.

Treatment-related Adverse Events

A summary of TEAEs will be presented for the Safety Analysis Set, including the number and percentage of subjects reporting at least one TEAE, the number and percentage of subjects with the following:

- Related TEAEs
- SAEs
- Related SAEs
- TEAEs with an outcome of death
- TEAEs
- Severe TEAEs
- TEAEs leading to RBP-6000 discontinuation

A breakdown of the number and percentage of subjects reporting each TEAE categorized by SOC and PT coded per the MedDRA dictionary version 19.0 will be presented in the Safety Analysis Set. Note that counting will be by subject not by event and subjects will be only counted once within each SOC or PT.

A further tabulation of events experienced by $\geq 5\%$ of subjects by SOC and PT will be presented for the Safety Analysis Set. If there are no TEAEs experienced $\geq 5\%$ of subjects by any PT, this table will be empty.

A summary of events reported, categorized by severity, will also be provided. Subjects with multiple events within a SOC or PT will be counted under the category of their most severe event within that SOC or PT. A further tabulation of severe AE/TEAEs will be presented by SOC and PT.

Additionally, treatment-related AEs/TEAEs will be summarized by maximum severity (mild, moderate, or severe). A breakdown of severe treatment-related AEs/TEAEs by SOC and PT will be provided.

All AEs (including non-TEAEs) recorded on the CRF will be listed.

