12.1.4 Deaths

A table presenting the number and percentage of subjects who died during the Treatment Period will be presented for the Safety Analysis Set, respectively. Deaths occurring in the study will also be listed for all screened subjects, if death occurs within the study.

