14.3 Safety Data Tables & Figures

Table 14.3.1.1 Overall Summary of Treatment-Emergent Adverse Events – Safety Analysis Set
Table 14.3.1.2 Summary of Treatment-Emergent Adverse Events by MedDRA System Organ Class and Preferred Term During the Treatment Period – Safety Analysis Set
Table 14.3.1.3 Summary of Treatment-Emergent Adverse Events Experienced by >=5% of Subjects by MedDRA Preferred Term During Treatment Period– Safety Analysis Set

Table 14.3.14 Summary of Treatment-Emergent Adverse Events Leading to Discontinuation by MedDRA System Organ Class and Preferred Term During Treatment Period- Safety Analysis Set

Table 14.3.1.5 Summary of Deaths due to Adverse Event (AE) - Safety Analysis Set

Table 14.3.1.6 Summary of Serious Treatment-Emergent Adverse Events by MedDRA System Organ Class and Preferred Term During Treatment Period- Safety Analysis Set

Table 14.3.1.7 Summary of Serious Treatment-Emergent Adverse Events Related to Study Treatment by MedDRA System Organ Class and Preferred Term During Treatment Period- Safety Analysis Set

Table 14.3.1.8 Summary of Treatment-Emergent Adverse Events by Maximum Severity, MedDRA System Organ Class and Preferred Term During Treatment Period – Safety Analysis Set

Table 14.3.1.9 Summary of Treatment-Emergent Adverse Events Related to Study Treatment by Maximum Severity, MedDRA System Organ Class and Preferred Term During the Treatment Period- Safety Analysis Set

Table 14.3.1.10 Summary of Severe Treatment-Emergent Adverse Events Related to Study Treatment Leading to Discontinuation by MedDRA System Organ Class and Preferred Term During the Treatment Period- Safety Analysis Set

Table 14.3.1.11 Summary of Severe Treatment-Emergent Adverse Events by MedDRA System Organ Class and Preferred Term During the Treatment Period- Safety Analysis Set

Table 14.3.1.12 Summary of Treatment-Emergent Adverse Events Potentially Pertaining to Drug Withdrawal Symptoms by MedDRA System Organ Class and Preferred Term During the Treatment Period- Safety Analysis Set

Table 14.3.1.13 Summary of Treatment-emergent Adverse Events Potentially Pertaining to Drug Withdrawal Symptoms During the Safety Follow-up Period for Subjects Who Entered into the Safety Follow-up Period

Table 14.3.1.14 Summary of Treatment-Emergent Adverse Events Potentially Pertaining to Injection Site Reactions by MedDRA System Organ Class and Preferred Term During the Treatment Period- Safety Analysis Set

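### With no EOS/ET visit, the Treatment Period stops at last injection + 28 days, up to 7 days short of the protocol's own window, so events at +29 to +35 leave the TEAE, serious-TEAE and death tables

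*SAP*

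**What the plan says.** SAP 20.1 sets the Treatment End Date as "the maximum of the date of the end-of-study/ Early Termination (EOS/ET) visit and the date of last injection + 28" days, and adds that "any records collected after the Treatment End Date will be considered as Safety Follow-up records". Three safety outputs depend on that date:

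- **TEAEs** (SAP 12.1.1) are events that "started following the first dose of RBP-6000 and before the Treatment End Date", or earlier events that worsened within the Treatment Period.
- **Deaths** (SAP 12.1.4): the table gives the "number and percentage of subjects who died during the Treatment Period".
- **SAEs** (SAP Appendix 3, Table 14.3.1.6): the title is "Summary of Serious Treatment-Emergent Adverse Events by MedDRA System Organ Class and Preferred Term During Treatment Period". Table 14.3.1.7, for related SAEs, is limited in the same way.

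The only AE table planned for the Safety Follow-Up Period covers drug-withdrawal symptoms (SAP 12.1.5, Table 14.3.1.13). All deaths, SAEs and AEs are listed for all screened subjects (Listings 16.2.13 to 16.2.15).

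On timing, Protocol 5.3 has injections "separated by a minimum of 26 days and a maximum of 35 days (28 days -2/+7 days"). The Schedule of Events gives the EOS visit the same -2/+7 window.

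**The concern.** If there is no EOS/ET visit, only the +28 term is left in the rule. A subject at +29 to +35 may still be waiting, on schedule, for the next injection or for EOS. An event in those days is nonetheless assigned to follow-up. The same event in a subject who later attends an injection or an EOS/ET visit is counted as on treatment.

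Classification therefore depends on later attendance, and death rules that out. Safety monitoring is half of the study's single objective and the safety tables are its main output. A rule that can remove the gravest events from those tables pushes the counts in one direction, downward.

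**Working it through.** **1. The plan's own figures.** From 28 days -2/+7: 28 - 2 = 26 and 28 + 7 = 35, which matches Protocol 5.3. Injection 6 falls on Day 1 + 5 × 28 = 141 and EOS on Day 1 + 6 × 28 = 169, which matches the Schedule of Events. An on-schedule EOS is therefore at last injection + 28, and the permitted window runs to +35.

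**2. The rule applied.** Days are counted from the last injection; in the third row, from the injection before it.

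| Situation | Treatment End Date | Days up to +35 left out |
|---|---|---|
| No EOS/ET visit | +28 | +29 to +35 (7 days) |
| EOS/ET visit at +35 | +35 | none |
| Next injection given at +35 | 35 + 28 = +63 | none |

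For TEAEs, SAP 12.1.1 says before the end date. Read literally, that also drops onset on +28, making 8 days.

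**3. Onset date against death date.** TEAE status follows onset; the 12.1.4 count follows the date of death. With no EOS/ET visit:

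- Fatal AE with onset and death on +31: not a TEAE, not a serious TEAE, not in the 12.1.4 count. Listings only.
- Fatal AE with onset on +25 and death on +30: still a TEAE with fatal outcome, but not in the 12.1.4 count. Two safety tables then disagree about the same subject.

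**4. Comparison with the protocol.** Protocol 6.9.2 defines a TEAE by start or worsening after IMP initiation, with no last-dose cut-off. Protocol 9.5.1.1 excludes only AEs that began after the EOS visit, and a subject with no such visit has no date to trigger that exclusion. The +28 limit is thus a narrowing, while the SAP's section on changes to protocol analyses reports none.

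**5. Size.** The uncovered share of the longest permitted interval is 7/35 = 20%. That assumes constant risk and no re-injection before +35. Let f be the fraction who would have been re-injected by Day 28 (not in the documents), counted as at risk for 28 days. The share is then about 7(1 - f)/[28 + 7(1 - f)]:

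- f = 0: 7/35 = 20%
- f = 0.5: 3.5/31.5 = 11%
- f = 0.8: 1.4/29.4 = 5%

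For an assumed 3 deaths in final intervals without an EOS/ET visit, the chance that at least one misses the 12.1.4 count is 1 - 0.80³ = 49% at f = 0, 1 - 0.889³ = 30% at f = 0.5 and 1 - 0.952³ = 14% at f = 0.8. For one death it is 20%, 11% and 5%.

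In person-time, if 2% to 20% of 300 subjects have no EOS/ET visit (assumed), that is 6 to 60 subjects. They contribute 6 × 7 = 42 to 60 × 7 = 420 uncovered person-days, or 0.11 to 1.15 person-years.

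**The case against.** The +28 rule has a rationale. It equals the nominal dosing interval, Protocol 5.2 describes release over roughly 28 days, and the SAP uses the same figure for exposure (10.1) and concomitant medications (9.3). The -2/+7 can be read as scheduling tolerance only. This stands as an explanation of the choice. It does not justify a hard stop, because the rule already counts events beyond +28 whenever an EOS/ET visit comes later.

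Nothing leaves the report. Every death, SAE and AE is listed, and in an uncontrolled study of about 300 subjects single deaths stay visible. This stands and limits the importance of the point. Incidence and death counts are still read from tables.

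Protocol 3.3 requires dosed subjects who discontinue to complete the EOS/ET visit, so few should lack one. This also stands. A reader might infer that hospitalisation causes the same loss; it does not if the subject later attends, because the late visit extends the period.

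The SAP is not uniform either. The title of the deaths table (14.3.1.5) carries no Treatment Period limit, and the text of 12.1.2 does not confine SAEs to TEAEs. The loss from the tables is therefore clear under the 12.1.4 text and the SAE table titles, but not under every sentence.

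A reader might also infer that the cut-off should be +35 for everyone. The documents do not support that. An on-schedule completer has EOS at +28, so the Treatment Period would run to Day 141 + 35 = 176, seven days past EOS. That conflicts with Protocol 9.5.1.1 and would move post-EOS withdrawal events out of the follow-up table.

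**Conclusion.** The point holds for one group: subjects with no EOS/ET visit, in the interval after their last injection. For them up to 7 permitted days (8 for TEAEs on the literal wording) fall outside the Treatment Period. AEs and SAEs starting then leave the TEAE and serious-TEAE tables, and deaths then leave the 12.1.4 count. A fatal AE that began before +28 stays a TEAE with fatal outcome even if the death is later.

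The 7-day gap is exact. The 20%, and the 49% for three deaths, are upper-bound illustrations. A reader might take them as the expected loss, but the documents give no death rate, no rate of missed EOS/ET visits and no distribution of actual injection intervals. The number of events affected is probably small. It matters because deaths are rare, so one omission changes the table, and because the omission is related to the outcome.

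**What to change.** - **SAP 20.1 and 12.1.1:** for subjects with no EOS/ET visit only, set the Treatment End Date for the AE, SAE and death tables to last injection + 35 days, and count events on or before it. Literal use of before would still lose +35. Start these subjects' follow-up AE table the next day, so that no event is counted twice.
- **Leave unchanged:** the rule for subjects who have an EOS/ET visit, and the exposure, urine drug screen and concomitant-medication windows.
- **SAP 12.1.4 and Table 14.3.1.5:** make text and title agree by showing all deaths in the Safety Analysis Set, split by Treatment Period and Safety Follow-Up. Align the SAE text in 12.1.2 with its table titles in the same edit.
- **SAP section on changes from the protocol:** state that a last-injection cut-off has been added.

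The cost is a few sentences, one extra derived date and slightly less favourable counts. Part of the dependence on attendance remains, because an event after +35 with no EOS/ET visit is still outside the Treatment Period. The all-deaths table covers that for deaths. No dosing or visit rule is affected.
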